Investigational Devices:	i-gel, King, LMA (Supreme and Unique)
Trial Sites:	
 University of Pittsburgh, University of Pittsburgh Medical Center, PI [name], Co-PI [name] Additional sites: Please see Appendix I
IDE Sponsor:	[name], MPH
Study Aims:	
AIM#1: To compare the effect of a standard strategy of airway management vs. a strategy of first attempt with supraglottic airway (SGA) upon 24- hour survival after traumatic injury.
 
AIM#2: To compare the effect of a standard strategy of airway management vs. a strategy of first attempt with supraglottic airway (SGA) upon hospital survival after traumatic injury.
 
AIM#3: To compare the effect of a standard strategy of airway management vs. a strategy of first attempt with supraglottic airway (SGA) upon major adverse events after traumatic injury.

Study Design:	Open label, multi-center, stepped wedge randomized trial comparing a standard airway management strategy and a strategy of initial use of SGA for airway management of prehospital trauma patients
Planned Sample Size:	2,009
Planned Study Time:	5 year study with 4 years of enrollment
Major Inclusion Criteria:	
 1. Traumatic injury requiring advanced airway management 2. Transporting (or intended transport) to an enrolling LITES Trauma Center
Major Exclusion Criteria:	
 1. Less than 15 years of age 2. Pregnancy 3. Prisoner 4. Initial advanced airway attempted by non-PACT provider 5. Cardiac Arrest without return of spontaneous circulation (ROSC) at the time of the intervention 6. Caustic substance ingestion 7. Airway burns 8. Objection to study voiced by subject or family member at the scene
Primary Endpoint:	24-hour survival

1. OBJECTIVE, SPECIFIC AIMS, BACKGROUND, AND SIGNIFICANCE

1.1 OBJECTIVE

Compare standard strategies of advanced airway management to a strategy of initial supraglottic airways in trauma patients within the prehospital setting.

1.2 SPECIFIC AIMS

Airway, Breathing, and Circulation (ABC) support is the prevailing strategy for the management of trauma. Current trauma resuscitation guidelines rank airway management among the highest clinical priorities¹. The standard approach to prehospital advanced airway management is endotracheal intubation (ETI). However, ETI is difficult and error-prone^{2,3}. Delays in airway management have been associated with increased morbidity and mortality. The use of ETI in trauma cases is controversial, and ETI is associated with increased mortality in traumatic brain injuries (TBI)^{4,5}. Intubation requires a high burden of training and most Emergency Medical Services (EMS) personnel have limited ETI skill and experience^{6,7}.

Alternatives to standard advanced airway management include supraglottic airways (SGA) such as the laryngeal tube, i-gel, and laryngeal mask airway. Compared with standard management, SGAs are simpler to insert, an easier skill to learn, and can provide adequate ventilation⁸⁻¹⁰. However, the comparative effectiveness of prehospital SGA and standard management in trauma patients is unknown.

LITES Task Order 0005 aims to compare different strategies of trauma airway management in the prehospital setting with the following aims:

AIM #1: To compare the effect of a standard strategy of airway management vs. a strategy of first attempt with supraglottic airway (SGA) on 24-hour survival after traumatic injury.

Hypothesis #1: The null hypothesis is that 24-hour survival is similar between standard strategy and initial SGA strategy.

AIM #2: To compare the effect of a standard strategy of airway management vs. a strategy of first attempt with supraglottic airway (SGA) on hospital survival after traumatic injury.

Hypothesis #2: The null hypothesis is that hospital survival is similar between standard strategy and initial SGA strategy.

AIM #3: To compare the effect of a standard strategy of airway management vs. a strategy of first attempt with supraglottic airway (SGA) on major adverse events.

Hypothesis #3: The null hypothesis is that the incidence of major adverse events is similar between standard strategy and initial SGA strategy.

1.3 BACKGROUND and SIGNIFICANCE

Prehospital trauma airway management is a low frequency, high consequence event

for both military and civilian providers. Airway management failures account for 8 to 15% of combat deaths deemed to be potentially preventable¹¹⁻¹³. Prehospital airway management consists of some combination of basic airway maneuvers and bag valve mask (BVM) ventilation to temporize the patient, followed by advanced management with either ETI, SGA, or a surgical airway (SA) procedure. While ETI is the gold standard in prehospital airway management, its safety and efficacy have been questioned, particularly following trauma and traumatic brain injury⁵. However, other investigators have demonstrated associations between survival and ETI in trauma patients, resulting in equipoise based on the existing literature¹¹.

In both civilian and military prehospital environments, the acquisition and maintenance of the skills necessary for airway management are exceptionally difficult. Previous studies on ETI have indicated that prehospital providers require 10 or more intubations to obtain proficiency and approximately 5 to 12 intubations per year to maintain proficiency⁷. Yet, the average prehospital provider performs fewer than two interventions per year⁶. Lairet et al. describe ETI as the most frequently missed lifesaving intervention, accounting for 53% of missed interventions in combat¹². The reasons for ETI failure are complex and include patient, provider, and environmental factors¹³.

The current alternative used in military airway management is surgical airway procedures. While these account for only 1.8% of military prehospital airway procedures, they account for 12% of missed lifesaving interventions. While the success of the procedure is as high as 82%, SA is also a rare procedure for which training and experience are limited¹².

[figure not shown]
SGAs have been shown to require less time and less practice to achieve proficiency to place^{8,9}. Although older devices performed poorly in military use, newer devices may have several advantages over standard management strategies, including ETI. The devices in the newer generation have simplified insertion procedures, lack balloons, do not require syringes for inflation, and have ports that allow for venting and decompression of the stomach.

In addition to their speed and ease of use, SGAs can be placed blindly without the need for the additional equipment required for a laryngoscopy. In tactical situations, blind insertion techniques may limit tactical exposure and improve light discipline¹⁴. SGAs have been associated with shorter prehospital scene times, which may translate into reduced risk for the provider and decreased patient mortality. Use of SGAs may also be a less perishable skill than the use of ETI, allowing for better retention and faster pre-deployment training.

2. RESEARCH DESIGN AND METHODS

2.1 CLASSIFICATION AND METHODOLOGICAL DESIGNS

We propose the LITES Task Order 0005 Prehospital Airway Control in Trauma (PACT) trial, a 5-year (4-year enrollment), open label, multi-center, stepped wedge randomized trial comparing standard airway management strategy and a strategy of initial use of SGA for the airway management of prehospital trauma patients (Figure 1). The trial will be carried out at sites within the LITES Network. The LITES Network is an operational trauma center consortium with the expertise, track record, and confirmed capabilities to conduct prospective, multicenter, injury care and outcomes research relevant to the U.S. Department of Defense.

Figure 1. Time Table

2.1.1 Randomization

PACT will employ a stepped wedge design (Figure 2) in which all participating EMS agencies transition from the control arm, standard airway management strategy, to the intervention arm, initial SGA strategy, with some agencies applying the intervention before others¹⁵. Once an agency has stepped to the initial SGA arm, they will remain assigned to this arm for the remainder of the study. Blinding is not possible with this intervention. This trial design allows us to perform a pragmatic trial for an intervention strategy that has agency level variation as a result of differences in provider makeup (EMT/paramedic, dual paramedic, paramedic/nurse), transport mode (air/ground), the availability of rapid sequence intubation (RSI), the use of adjuncts (oropharyngeal and nasopharyngeal airways, tracheal introducers, video laryngoscopy), and training.

The trial will be conducted over approximately 48 months with 17 prehospital agencies crossing from standard care arm to intervention arm in one of seven periods. 287 subjects will be enrolled in each enrollment period, before stepping to the next enrollment period. This will continue until 1,722 subjects are enrolled, when all prehospital agencies will be exposed to the intervention arm.

Figure 2. Schematic illustration of the PACT stepped wedge randomized trial with six steps.

Approx. time	Year 1		Year 2		Year 3		Year 4	
Enrollment period →	287 subjects	574 subjects	861 subjects	1,148 subjects	1,435 subjects	1,722 subjects	2,009 subjects	
Step number ↓								
1								
2								
3								
4								
5								
6								

	Standard care (control arm)
	Initial SGA (intervention arm)

2.2 BRIEF DESCRIPTION OF STUDY DESIGN

Standard Care Arm: Airway management in the standard care arm of this pragmatic trial will be dictated by local protocols. We will accrue data on all participants who met all the inclusion criteria and none of the exclusion criteria regardless of which airway management strategy is utilized.

Initial SGA Arm: EMS agencies randomized to the intervention arm will follow a strategy of initial advanced airway management with an SGA. Airway management of eligible subjects will be initiated at any time between EMS initial contact and the transfer of care to the receiving trauma center. Only the initial advanced prehospital airway management strategy is dictated by the study protocol; all other interventions, including preparation and subsequent attempts at advanced airway management, will be dictated by local protocols.

In the event that a prehospital provider is unable to complete preparations, such as bag valve mask ventilation, and place an advanced airway, the subject will be retained and analyzed according to the intended arm assignment.

In both arms, study data will be abstracted from EMS records, including indications for airway management, vital signs, use of adjuncts, pharmacological treatment, and timing of interventions and will be entered into an electronic data management system.

2.3 COORDINATION OF STUDY

2.3.1 Clinical Coordinating Center (CCC)

Clinical Coordination specific to the PACT trial will be performed by LITES Network Coordinating Center and its dedicated research team at the University of Pittsburgh. The CCC's responsibilities include all regulatory requirements, provider and coordinator training, and clinical monitoring.

2.3.2 Data Coordinating Center (DCC)

Data Coordination specific to the PACT trial will be performed by the Epidemiology Data Center (EDC), led by [name] at the Graduate School of Public Health at the University of Pittsburgh. The DCC will design data collection forms, build and maintain an electronic data management system, provide training and technical assistance for site-based data entry personnel, develop and implement quality control mechanisms (including in-person and remote monitoring), and produce reports. The DCC will also plan, coordinate, and carry out all statistical analyses and make the datasets available for public use after the trial is over.

2.3.3 Training and Participating Site Coordination

The CCC is responsible for all research coordinator training and prehospital provider training. Research coordinators, prehospital providers, and associated staff will be trained during the months prior to the trial start date on the scientific basis for the trial, specific inclusion and exclusion criteria, data collection and processing, prehospital procedures, and standard operating procedures (SOPs). Training verification and retraining will occur if new staff members are hired at individual participating sites. Trial enrollment will be tracked monthly using the web-based data platform. Screening, enrollment, and data completeness and accuracy will be assessed via a site visit (in-person or remotely) initially after the first three subjects are enrolled. Subsequent monitoring visits will then occur at least twice annually.

During the site initiation visit and the visit prior to the site switching strategies, we will review the participating EMS agencies' airway protocols. Specifically, we will reinforce the assessment and treatment of inadequate ventilation using an advanced airway. We will review recognition and treatment of incorrect placement of the device, dislodgements, air leak and possible laryngospasm. We will review strategies for management of patients who have vomited at any time during the prehospital period including suctioning and gastric decompression following the placement of the advanced airway. We will address sedative and analgesic medication administration to facilitate advanced airways in accordance with the EMS agencies' local protocols. All EMS agencies will review absolute and relative contraindications to advanced airway placement including but not limited to caustic ingestion, inability to open the mouth, and gagging on insertion of the device.

2.4 STUDY DEVICES

2.4.1 Study Device Dispensing

As part of the pragmatic design of the study, prehospital services will continue to utilize the specific airway management devices that are already in use and in supply at their respective agencies. Although the SGAs used on enrolled subjects during the interventional arm will be considered investigational devices, they will not be provided by the study.

2.4.2 Device Selection

The study will focus on airway management strategies using second generation SGAs as our intervention. Second generation SGAs have fewer fail points than the previous devices. Additionally, prehospital providers have a higher first pass success rate and novice users generally find the devices easier to place, decreasing the amount of training required and lessening the burden of skill maintenance. SGAs employ a rapid, blind technique for placement that requires less equipment than endotracheal intubation. SGAs also provide a less invasive airway management strategy which may allow the provider to focus on other time dependent tasks.

To emphasize the comparison of the airway management strategy rather than the individual device, EMS agencies will continue to use the device they currently have in service. As a pragmatic trial we will not ask them to change devices or training regimens. We plan *a priori* subgroup analyses to examine differences in SGA type used within the intervention strategy.

2.4.3 Device Accountability

SGAs used in enrolled subjects will be tracked per FDA requirement. As these devices are already in use by the prehospital services per their standard care protocols and will not be provided to the agencies by the study, we will only be tracking the individual devices that are used in enrolled subjects in the investigational arm. Tracking of these study devices will be consistent with record-keeping and other responsibilities as required under 21 CFR 812.

2.4.4 Rescue Strategy

Only the initial attempt at advanced airway management is dictated by study protocol. All subsequent attempts at management will be at the provider's discretion and will be based on local protocol.

2.5 STUDY ENDPOINTS

Primary Outcome: The primary outcome for the trial is 24-hour survival.

Secondary Outcomes: Secondary outcomes include survival to hospital discharge, expected clinical events (including incorrect placement of the airway, inadequate ventilation, airway trauma, or concern for aspiration as defined as documented vomiting and/or need for suctioning), airway management performance (including initial pass success, overall success, and use of rescue technique), ICU length of stay, ventilator days, and expected adverse events including airway trauma, pneumothorax, incidence of acute respiratory distress syndrome (ARDS) and incidence of ventilator associated pneumonia (VAP).

Primary Outcome Definition:

24-hour Mortality: A binary variable defined as death within 24 hours

Secondary Outcome Definitions:

Secondary outcomes will be assessed from arrival at the trauma center through day 30 or discharge, whichever is first.

In-Hospital Mortality: A binary variable defined as death recorded any time after hospital arrival.

Airway Management Performance: The elements of airway management performance include airway misplacement (including endotracheal tube misplacement), initial pass success (the successful placement of device on the first attempt past the teeth confirmed by EtCO₂), sequence of airway insertion, airway insertion success and time, number of airway insertion attempts, inadequate ventilation, and any instances of airway conversion (change of airway in the first 24 hours).

Acute Respiratory Distress Syndrome (ARDS): The Berlin definition for mild ARDS ($\text{PaO}_2/\text{FIO}_2 \leq 300$ mm Hg plus timing, imaging, and origin criteria) will be utilized as a threshold value to determine the incidence of ARDS within 24 hours of presentation. We will further stratify patients into mild, moderate ($\text{PaO}_2/\text{FIO}_2 \leq 200$ mm Hg), or severe ($\text{PaO}_2/\text{FIO}_2 \leq 100$ mm Hg) ARDS.¹⁶

ICU length of stay (LOS): Defined as the number of days spent admitted to the Intensive Care Unit. ICU LOS will be recorded to the first decimal place.

Ventilator Days: Defined as number of days on a mechanical ventilator. Ventilator days will be recorded to the first decimal place.

Ventilator Associated Pneumonia: A binary variable defined as VAP in the first 24 hours as evident by a new infiltrate on chest image and ≥ 1 of the following: temp >38 or less than 36 degrees C, WBCs $>12,000$, purulent secretions from the airways and or reduction in gas exchange ($\text{PaO}_2/\text{FIO}_2 \leq 300$ mm Hg). (Michetti Trauma 2012)

Other Adverse Events: Binary variables defined as the onset of one of the following adverse events in the first 24 hours after enrollment: oropharyngeal trauma, hypopharyngeal trauma, pneumothorax, aspiration pneumonitis, ARDS, and VAP.

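### The prehospital aspiration outcome has no time anchor and no rule for suctioning, and it conflicts with the stated assessment window; it can mislead in either direction

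*Combined protocol and SAP*

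**What the plan says.** Section 2.5 of the combined protocol and SAP names several expected clinical events as secondary outcomes. One is "concern for aspiration as defined as documented vomiting and/or need for suctioning". Nothing in 2.5 or elsewhere says whether the vomiting or suctioning must follow the airway attempt, or what the suction must have been for.

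Section 2.5 then sets one window for all secondary outcomes: "Secondary outcomes will be assessed from arrival at the trauma center through day 30 or discharge, whichever is first".

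A separate list of other adverse events, with onset in the first 24 hours after enrollment, contains "oropharyngeal trauma, hypopharyngeal trauma, pneumothorax, aspiration pneumonitis, ARDS, and VAP". ARDS and VAP have definitions in 2.5; aspiration pneumonitis has no diagnostic criteria.

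The trial is unblinded (2.1.1), and prehospital data in both arms are abstracted from EMS records (2.2).

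**The concern.** Whether a strategy leads to more or less aspiration is a natural safety question in this comparison, and this item is the only prehospital measure of it. As worded, it can count a patient who vomited before the crew arrived, or one suctioned for facial bleeding, as well as one who regurgitated after the device went in. Only the last could be a consequence of the strategy.

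Two different errors follow. Events before the attempt, if equally frequent in both arms, pull the observed difference towards zero. Suction for reasons other than aspiration may depend on the technique used, and then it biases the comparison. The mixed model that 2.6.1 applies to binary secondary outcomes, with a random effect for randomization unit and a fixed effect for step, does not remove a coding difference that travels with the arm.

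The window sentence adds a contradiction. Two abstractors could code the same chart in opposite ways and each point to section 2.5.

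**Working it through.** **Reading the window against the item.** The documents give no rate, effect size or power for this outcome, so there is no planned figure to reproduce.

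- If the window governs, only vomiting and suctioning after trauma-center arrival count. That misses the prehospital phase. It would also exclude initial pass success, number of attempts and insertion time, which 2.5 lists as secondary outcomes although 3.3 says the interventions are completed before hospital arrival.
- If the window does not govern, the item has no start point. Everything documented by the crew can count, including events before the attempt.

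Neither reading gives a usable definition.

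**Illustration.** Every rate here is an assumption. Let *a* be the true event rate during or after the attempt, *b* the pre-attempt rate of vomiting or suctioning (equal by arm), and *s* the rate of suction unrelated to aspiration. Taking these as independent,

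recorded rate = 1 − (1 − b)(1 − s)(1 − a).

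Take a = 5% in the standard arm and 10% with SGA, so SGA is truly 5 points worse.

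*Dilution only (s = 0 in both arms).* The difference is (1 − b)(0.95 − 0.90) = 0.05(1 − b). For b = 20%, 30% and 40% this is +4.0, +3.5 and +3.0 points. It shrinks but cannot change sign.

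*Unrelated suction differing by arm (b = 30%).* The standard arm at s = 15% is 1 − 0.70 × 0.85 × 0.95 = 43.5%. The SGA arm is 1 − 0.70 × (1 − s) × 0.90. Differences are taken before rounding.

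| s standard | s SGA | Recorded standard | Recorded SGA | SGA − standard |
|---|---|---|---|---|
| 0% | 0% | 33.5% | 37.0% | +3.5 |
| 15% | 0% | 43.5% | 37.0% | −6.5 |
| 15% | 15% | 43.5% | 46.5% | +3.0 |
| 15% | 25% | 43.5% | 52.8% | +9.3 |

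With none in the SGA arm, b = 20% and s = 10% in the standard arm give 31.6% versus 28.0% (−3.6 points). With b = 40% and s = 25% they give 57.3% versus 46.0% (−11.3 points).

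*Where the sign reverses.* The recorded difference favours SGA when (1 − s_std) × 0.95 < (1 − s_SGA) × 0.90, that is, when s_std > 1 − (1 − s_SGA) × 0.90/0.95. For s_SGA = 0 the threshold is 5.3%; for s_SGA = 10% it is 14.7%. The threshold does not depend on b.

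*Where the harm is exaggerated.* With b = 30% and s_std = 15%, the recorded excess passes the true 5 points once 0.63 × (1 − s_SGA) < 0.56525 − 0.05, that is, s_SGA > 18.2%.

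*Other base rates.* With a = 10% versus 15% and b = 20%, the threshold with no SGA-arm suction is 1 − 0.85/0.90 = 5.6%. Unrelated suction of 10% versus 0% gives 35.2% versus 32.0% (−3.2 points); 10% versus 20% gives 35.2% versus 45.6% (+10.4 points).

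**The case against.** A reader might infer that the definition favours SGA: laryngoscopy needs a clear view, whereas section 1.3 says "SGAs can be placed blindly without the need for the additional equipment required for a laryngoscopy", so the standard arm would collect more suction events. The documents do not support that direction.

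- No section mentions suction to obtain a view, and none gives a suctioning rate by technique. The item refers to a need for suctioning, which is narrower than any suctioning.
- The standard arm is not uniformly laryngoscopy: "Airway management in the standard care arm of this pragmatic trial will be dictated by local protocols". Attempts after the first in the SGA arm also follow local protocols (2.4.4) and may include laryngoscopy.
- Suction may also be recorded in the SGA arm. Section 1.3 says newer devices "have ports that allow for venting and decompression of the stomach", and the training in 2.3.3 covers "management of patients who have vomited at any time during the prehospital period including suctioning and gastric decompression following the placement of the advanced airway".
- That training is given at site initiation and again before an agency switches, so both arms receive it. If the second review raises documentation, it raises recorded events in the SGA arm and counts against SGA.

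All of this stands. The cases that reverse in favour of SGA put no unrelated suction in the SGA arm; equal or higher suction there removes or turns round the effect.

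It is also fair to say that aspiration pneumonitis is a separate outcome. The mitigation is partial: it lacks criteria, its clock starts at enrollment, which 3.3 defines as time on scene and so can precede the attempt, and it needs hospital data that 5.1 does not expect for subjects taken to non-participating hospitals.

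Finally, this is one secondary item. It is neither the primary outcome nor part of the interim safety composite in 2.6.6. That limits its weight but does not make it interpretable.

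**Conclusion.** The point holds as a defect of definition. The item is a non-specific proxy with no time anchor and no suction rule, and section 2.5 contradicts itself on whether prehospital events count at all.

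Pre-attempt events dilute a true difference if they are equal by arm. That equality is itself an assumption, because crews identify patients while knowing the agency's current arm. Unrelated suction can bias the comparison in either direction. Under assumed true rates of 5% and 10%, about 5.3% of unrelated suction in the standard arm alone is enough to reverse the sign; a sufficient excess in the SGA arm overstates the harm.

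These figures rest on assumed rates and independence. They show that modest differences matter, not which way the trial's result would lean. The conclusion that SGA would look falsely safe does not follow. The 24-hour survival analysis is unaffected.

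**What to change.** In section 2.5:

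1. Define the outcome as new vomiting or regurgitation documented after the start of the first advanced airway attempt and before transfer of care. Avoid a criterion that depends on seeing gastric contents in the airway, since laryngoscopy offers a view that blind insertion does not.
2. Record vomiting or suctioning before the attempt as a yes/no baseline variable in both arms, and report it by arm.
3. Report suctioning as a separate item by recorded indication, not as aspiration on its own.
4. Keep the present composite as a sensitivity analysis.
5. Amend the window sentence so that prehospital secondary outcomes have a prehospital window.
6. Give diagnostic criteria for aspiration pneumonitis.
7. State how subjects with no advanced airway attempt, whom 2.2 retains, are coded.

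The cost is some wording and a before/after field with an indication on the abstraction form; 2.6.9 already collects times and descriptions of prehospital interventions. The downside is fewer events, and some charts will not time the vomiting clearly, so a code for unknown timing is needed.

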Hypothesis #1: For the primary outcome, an indicator of death within 24 hours will be generated for each participant. A generalized linear mixed model (i.e. logistic regression model) will be used to assess the independent impact of initial SGAs on 24-hour survival, with a random effect of randomization unit a fixed effect for each step, and fixed effects of airway management (standard vs. initial SGA) and the potential confounding effects of baseline characteristics. The estimated intra-randomization unit correlation and time effect from this model will be reported to help design future randomized trials and to describe the potential confounding effects of calendar time. For time-to-event data, a mixed effects Cox-proportional hazards regression model will be used to assess the independent impact of airway management strategy on time to death, with randomization unit as a random effect and step, airway management strategy, and the potential confounding effects of baseline characteristics not balanced through random assignment as fixed effects.

Hypothesis #2: The same analytic approach that was carried out for hypothesis #1 will be implemented, but the outcome of interest will be survival to hospital discharge.

Hypothesis #3: The analytic approach for the secondary outcomes will vary based on the type of outcomes. For binary outcomes (e.g., 24-hour and in hospital mortality, ventilator associated pneumonia, and post-traumatic ARDS), the same analytic approach that was carried out for Hypothesis #1 will be implemented. For continuous outcomes (e.g., hypotension or hypoxia dose) a generalized linear mixed model (i.e., linear model) will be used to assess the independent effect of airway management strategy on outcome, with a random effect of randomization unit, a fixed effect for each step, and fixed effects of airway management strategy (standard airway versus initial SGA) and the potential confounding effects of baseline characteristics.

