2.6.9 Data Elements

Prehospital Elements: To include (but not be limited to) scene time, vital signs, times and description of prehospital interventions, procedure type(s), device type(s), airway adjuncts used, rapid sequence intubation, associated medications and dosages used, number of procedure attempts, reason for failed attempt(s), progression to surgical airway, time to successful airway management, time to advanced airway, procedure complications, time and dose of any medications administered (for induction, post intubation sedation, and resuscitation), transport time, vital signs during transport, times and description of interventions provided during transport, and mode(s) of transport (e.g. ground, air). Also includes provider level data—including level of training—and system level data, including staffing, service volume, frequency of airway management, and ambulance location (rural/urban).

In-Hospital Elements: To include (but not be limited to) relevant vital signs, relevant laboratory studies (including arterial blood gases), and interventions (especially time to extubation and/or reintubation as applicable). Ventilator associated pneumonia, post-traumatic acute respiratory distress syndrome (ARDS), and patient disposition will also be collected.

Outcome Elements: To include (but not be limited to) 24-hour survival, hospital length of stay, length of stay in ICU, ventilator days, and in-hospital survival through day 30.

Exploratory Analyses: To include (but not be limited to) associations that may represent the underlying mechanisms associated with airway management's effect on 24-hour survival. When the necessary data are available, we will examine time to definitive airway, exposure to hypoxia,

superoxia, hypotension, hypocarbia and hypercarbia. Exposure will be examined as a categorical value and as a continuous variable calculated as a function of depth (calculated from a given normal value) times duration. The value of this expression will be regressed to look for an association with mortality.

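### Aim 2 has no single definition that settles deaths before hospital arrival, and ICU and ventilator days make no allowance for death

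*Combined protocol and SAP*

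**What the plan says.** Three descriptions of the Aim 2 outcome stand in the combined protocol and SAP.

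- Section 2.5 defines the variable from arrival: "In-Hospital Mortality: A binary variable defined as death recorded any time after hospital arrival". The sentence governing all secondary outcomes does the same: "Secondary outcomes will be assessed from arrival at the trauma center through day 30 or discharge, whichever is first".
- The list of secondary outcomes in Section 2.5 and the Hypothesis #2 text in Section 2.6.1 use a different label: "the outcome of interest will be survival to hospital discharge". The Hypothesis #3 text in Section 2.6.1 also names in-hospital mortality as a binary outcome to be modeled.
- Section 2.6.9 lists "in-hospital survival through day 30".

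Eligibility and enrollment are set earlier than arrival. Section 3.3 places enrollment at the enrolling agency's time on scene and says the interventions are finished before the patient reaches hospital. Section 3.2 accepts intended transport. The primary analysis is by intention to treat (Section 2.6.1).

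For duration outcomes, Section 2.5 has "Ventilator Days: Defined as number of days on a mechanical ventilator" and a matching count of days in the ICU. The only method given for continuous outcomes in Section 2.6.1 is a linear mixed model. No section says what value a patient who dies receives.

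**The concern.** The strategy under test is delivered before the Aim 2 clock starts. A patient can be enrolled, treated, included by intention to treat, and dead before arrival. That patient is a death for the primary outcome, and may or may not be one for Aim 2, depending on which description the analyst follows. The trial is open label, so this should not be decided once data are in hand. If deaths before arrival differ between arms, the choice changes the estimated effect.

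The day counts have a separate problem. A patient who dies in the first hours contributes almost no ICU or ventilator time. An arm that keeps more patients alive will therefore show more days even if the strategy does nothing to duration among survivors.

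**Working it through.** The plan states no figure of its own on this point, so there is none to reproduce. The only planning figures used are the 24-hour death rates in Section 2.6.2, 16.7% and 9.7%, a difference of 7.0 points.

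**1. The definitions side by side**

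| Patient | Survival to discharge (2.5 list, 2.6.1) | In-hospital mortality (2.5 definition) | In-hospital survival to day 30 (2.6.9) | 24-hour mortality (2.5) |
|---|---|---|---|---|
| Enrolled, dies before arrival | failure | not an event | not stated | death |
| Dies in hospital on day 35 | failure | death by the definition, but outside the stated window | survivor | survivor |

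The primary outcome carries no arrival condition: "24-hour Mortality: A binary variable defined as death within 24 hours". The imputation rule in Section 2.6.7 covers only 24-hour mortality, so it does not fill the gap for Aim 2.

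**2. Effect on Aim 2 if prehospital deaths differ by arm**

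Assumptions (none is in the documents): total mortality to discharge T = 20% in both arms, so no true difference; prehospital death rate q of 0-5% in the control arm, and 1 or 2 points higher with initial SGA.

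- Prehospital deaths coded as survivors: observed mortality = T - q. The false difference equals the imbalance, 1.0 or 2.0 points in favor of SGA.
- Prehospital deaths excluded: observed mortality = (T - q)/(1 - q).
  - q = 1% v 2%: 0.19/0.99 = 19.2% v 0.18/0.98 = 18.4%, a false difference of 0.8 points.
  - q = 5% v 7%: 0.15/0.95 = 15.8% v 0.13/0.93 = 14.0%, a false difference of 1.8 points.
- Equal q in both arms: the false difference is 0 under either coding.

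**3. Effect of ignoring death on ventilator days**

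Assumptions: 24-hour deaths are the only deaths; each contributes 0.5 ventilator day; survivors have the same mean L in both arms, taken as 3 to 10 days.

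Mean days in an arm with death rate p = 0.5p + L(1 - p). The SGA-minus-control difference is therefore (0.167 - 0.097)(L - 0.5) = 0.07(L - 0.5).

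- L = 3: control 0.0835 + 2.499 = 2.58; SGA 0.0485 + 2.709 = 2.76; difference 0.07 × 2.5 = 0.18.
- L = 10: control 0.0835 + 8.330 = 8.41; SGA 0.0485 + 9.030 = 9.08; difference 0.07 × 9.5 = 0.67.

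On a 30-day ventilator-free scale with death scored 0, the mean is (1 - p)(30 - L) and the difference is 0.07(30 - L): 1.89 days at L = 3 and 1.40 days at L = 10, both in favor of SGA. The direction reverses. The same algebra applies to ICU days.

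**The case against.** The strongest reply is that the Aim 2 label already answers the question. A patient who dies before arrival did not survive to discharge, and under intention to treat counts as a failure. A reader might infer from the arrival-based definition that Aim 2 simply drops these deaths, or that they disappear from the trial. The documents support neither. The labels conflict and nothing states which governs, and the powered 24-hour outcome counts the deaths. That part of the reply stands, and it limits the finding to a conflict with no coding rule.

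The affected group may also be small. Cardiac arrest without return of circulation at the time of the intervention is an exclusion (Section 3.3), and a patient who deteriorates in transit but is pronounced at the trauma center has a death recorded after arrival. With no rate in the documents, the number of such patients cannot be stated.

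A reader might also infer that the arrival-based window removes first-pass success and the other airway outcomes. It is better read as a wording slip. Section 2.2 draws the data from EMS records, Section 2.6.9 lists attempts, failures and times as prehospital elements, and Section 2.5 dates other adverse events from enrollment. Nor does any section say that the Cox model censors at discharge, so no fault can be found there.

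On day counts, the plan does not say that fewer days is better, raw days are a legitimate measure of resource use, and the examples given for the linear model are hypotension and hypoxia dose. Even so, these are listed secondary outcomes to be compared by arm, and no other method or rule for death is offered.

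**Conclusion.** The point holds as a secondary-endpoint correction. Aim 2 has descriptions that classify the same patient differently and no rule for death before arrival. The distortion is at most equal to the arm difference in prehospital deaths: the full amount if those deaths are coded as survivors, and 0.8-1.8 points for a 1-2 point imbalance if they are excluded, given the assumed 20% total mortality. With no true effect and no imbalance there is no distortion.

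ICU and ventilator days, compared as raw counts, would make the arm with fewer deaths look about 0.2-0.7 ventilator days worse in the plan's own target scenario. That size rests on the assumed survivor means, 0.5 day in early deaths and no effect among survivors; the direction needs only that early deaths have fewer days than survivors. The primary analysis and the sample size are unaffected.

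**What to change.** - **Aim 2.** Use one definition throughout Sections 2.5, 2.6.1 and 2.6.9: death from any cause from enrollment to hospital discharge or day 30, whichever is first, with prehospital deaths counted as deaths.
- **Non-participating hospitals.** Section 5.1 expects no in-hospital data for these subjects and mentions a vital-status search only for 24-hour mortality. Treat them as missing for Aim 2 unless vital status is obtained, and add a sensitivity analysis. It cannot be assumed that every input is already collected.
- **Window sentence.** Reword it so that prehospital airway outcomes run from enrollment. This is wording only.
- **ICU and ventilator days.** Analyze ICU-free and ventilator-free days to day 30, with death as the worst value, in an ordinal or rank-based mixed model. Keep raw days as description.

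The cost is mostly endpoint wording and derivation, plus any effort to obtain vital status for subjects taken elsewhere. Free-days are less intuitive and mix mortality with duration. Because follow-up ends at discharge, they also assume that patients discharged alive stay alive and off the ventilator to day 30; the plan should say so. A competing-risk analysis would be a workable alternative.
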